## 9 CONTENT OF REPORTS

The primary analysis is conducted when the Primary Cohort has been treated for 48 weeks (see Section 6.3). Longitudinal analyses present data on treatment through Week 48. Efficacy is focused on the Primary Cohort. Safety is focused on blinded therapy through Week 48 for treated subjects, as well as on all ETV therapy for the All ETV Safety Cohort. Follow-up safety is presented only if ≥ 10% of treated subjects have post-dosing follow-up data.

An additional analysis is performed when all subjects have reached Week 48. Longitudinal analyses present efficacy data on treatment through Week 48 for treated subjects, efficacy data on treatment through Week 96 for the Year 2 Primary Efficacy Cohort, safety data on treatment through Week 96 for the Year 2 Safety Cohort, and all available safety data on ETV treatment for the All ETV Safety Cohort. All safety analyses described in this plan are performed.

An additional unplanned analysis is performed when all subjects have reached Week 96. All analyses described in this plan are performed, except for pre-treatment analyses of study population and efficacy/safety analyses on blinded therapy through Week 48.

An additional analysis is performed when all subjects have completed study therapy. All analyses described in this plan are performed, except for pre-treatment analyses of study population, efficacy/safety analyses on blinded therapy through Week 48, and efficacy/safety analyses on treatment through Week 96.

The final analysis is performed when the last subject has completed long-term follow-up. At a minimum, safety analyses are reported for the off-treatment and long-term follow-up periods.

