## 4.3 Other Secondary Endpoints

- The number and percent of subjects with adverse events (including palatability issues), serious adverse events (SAEs), discontinuations due to adverse events, and HBV disease progression through Week 48;
- Proportions of subjects with HBeAg loss at Weeks 48 and 96;
- Proportion of subjects with HBeAg seroconversion at Week 96;
- Proportion of subjects who maintained HBeAg seroconversion at Week 96 (end of blinded therapy) among subjects who achieved HBeAg seroconversion at Week 48;
- Histological analysis among subjects with available liver biopsy.

[REDACTED]

- [REDACTED]

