Additional safety data will be contributed by PBO randomized subjects switching to open label ETV at study Week 52. Because it is expected to take 2 calendar years to randomize 123 subjects

and assuming steady enrollment over that time frame, the last PBO randomized subject will be completing Week 48 by study week 144. Assuming a 10% drop out per year, 18 of the 20 subjects randomized to PBO during the first calendar year will reach Week 48 by study Week 96; 16 of these 18 will be switched to open label ETV (assuming a 10% HBeAg seroconversion rate on PBO). With a 10% drop out rate per year, 14 of these 16 will be completing 48 weeks of open label ETV by study Week 144 and will be added to the integrated safety database. This will bring the number of subjects in the integrated safety database with at least 48 weeks of ETV exposure after two years of enrollment to approximately 110 subjects.

While the analysis of the primary endpoint is based on a randomized sample size of 123, the size of the overall study population has been augmented to 180 randomized subjects in order to meet the requirement of a health authority. Therefore the final safety dataset as described in the previous 2 paragraphs will also be augmented. The accrual of the first 123 randomized subjects is expected to take 2 years. Thereafter, the enrollment will remain open until 180 subjects are randomized. Additional re-analyses will be performed on the augmented population.

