### 6.3 Populations for Analyses

- **Enrolled subjects** are those who sign an informed consent form and are assigned a Patient Identification number (PID). This cohort is used to assess subject disposition, deaths and serious adverse events during the **pre-treatment period**.
- **Randomized subjects** are enrolled subjects who receive a treatment assignment from the central randomization center. This cohort is used to assess subject status and accrual.
- **Treated subjects** are randomized subjects who receive at least 1 dose of study therapy. This cohort is used to assess all data domains.
  - **Primary cohort** is defined as at least the first 123 subjects randomized and treated. The Primary Cohort is used for the primary analyses.
- **Off-treatment follow-up subjects** are treated subjects who discontinue study therapy and have at least 1 of the following assessments during the **off-treatment follow-up period** (see [Section 6.1](#)): death date if it exists; adverse event onset date; HBV related diagnosis date; vital signs date; physical measurement date; physical exam date; neurologic exam date; laboratory test date (safety, pregnancy, serology and virology); liver biopsy date; Tanner staging date. This cohort is used to assess safety during the off-treatment follow-up period.
- **Long-term follow-up subjects** are treated subjects who discontinue study therapy and have at least 1 of the following assessments during the **long-term follow-up period** (see [Section 6.1](#)): death date if it exists; adverse event onset date; HBV related diagnosis date; vital signs date; physical measurement date; physical exam date; neurologic exam date; laboratory test date (safety, pregnancy, serology and virology); liver biopsy date; Tanner staging date. This cohort is used to assess safety during the long-term follow-up period.
- **Alternative ETV follow-up subjects** are treated subjects who discontinue study therapy, receive at least 1 dose of alternative ETV therapy, and have at least 1 of the following assessments during the **alternative ETV follow-up period** (see [Section 6.1](#)): death date if it exists; adverse event onset date; HBV related diagnosis date; vital signs date; physical measurement date; physical exam date; neurologic exam date; laboratory test date (safety, pregnancy, serology and virology); liver biopsy date; Tanner staging date. This cohort is used to assess safety during the alternative ETV follow-up period.

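### At the primary analysis, crude through-Week-48 safety percentages for all treated children include those enrolled after the Primary Cohort, most of whom have under 48 weeks of treatment, so absolute risks come out too low at that cut

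*SAP*

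**What the plan says.** SAP section 9 sets the trigger: "The primary analysis is conducted when the Primary Cohort has been treated for 48 weeks". For that report it restricts efficacy ("Efficacy is focused on the Primary Cohort") but not safety: "Safety is focused on blinded therapy through Week 48 for treated subjects", with a further focus on entecavir exposure of any kind in the All ETV Safety Cohort.

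SAP section 6.3 defines the two sets. Treated subjects "are randomized subjects who receive at least 1 dose of study therapy"; the Primary Cohort "is defined as at least the first 123 subjects randomized and treated". SAP section 5 expects the first 123 to accrue in 2 years and then says: "Thereafter, the enrollment will remain open until 180 subjects are randomized".

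SAP section 7.6 closes each child's through-Week-48 safety period at 54 weeks or at first open-label entecavir, whichever comes first. It does not ask whether the child could yet have reached Week 48. Sections 7.6.2, 7.6.3, 7.6.5 and 7.6.6.1 use this period for serious adverse events, discontinuations due to adverse events, graded adverse events, laboratory abnormalities and ALT flares. Section 7.6.6 limits laboratory summaries to subjects with at least one measurement in the period.

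SAP section 4.3 lists adverse events, serious adverse events, "discontinuations due to adverse events, and HBV disease progression through Week 48" as a secondary endpoint. Protocol section 8.2 assigns adverse event analyses to the treated cohort.

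**The concern.** A percentage labelled through Week 48 will be read as a 48-week risk. At this cut part of the denominator has been observed for less than that, and no rule in the SAP deals with children whose Week 48 is not yet due. Events they have not yet had time to experience count as non-events. The error has one direction: absolute risks, and absolute differences between arms, are too small.

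This is the report that sets the safety percentages beside the primary efficacy result, so its absolute risks are likely to be the first ones weighed against benefit.

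**Working it through.** **The plan's own figure.** The documents give no figure for incomplete follow-up at this cut. The number they do give, 123, is the efficacy sample size, and it reproduces. With 82 and 41 children, 20% vs 1% and two-sided 0.05, the pooled proportion is (82 × 0.20 + 41 × 0.01)/123 = 0.137. The standard errors are 0.0657 (null) and 0.0468 (alternative), so power = Φ((0.19 − 1.96 × 0.0657)/0.0468) = 90.4%. That calculation is not in dispute.

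**Inputs.** From SAP section 5: 123 children in 2 years (104 weeks), so 123/104 = 1.18 per week; total 180, so at most 57 later children. Assumed, because the plan is silent: accrual after the 123rd child at 0.5, 1 or 2 times that rate; a data cut on the trigger date; no dropout; a 48-week horizon.

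**Formula.** Let *k* be the number of later children, with treatment time *t* spread evenly up to 48 weeks, and *p* the true 48-week risk. Then

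- λ = −ln(1 − *p*)/48^s, where s = 1 is constant hazard, s = 0.5 gives early events and s = 2 late events;
- *r* = mean of 1 − exp(−λ t^s) over the later children;
- printed percentage = (123*p* + *kr*)/(123 + *k*).

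**Planned rate, constant hazard.** *k* = 1.18 × 48 = 56.8; share incomplete = 56.8/179.8 = 31.6%. Later children average 24 weeks, so mean follow-up is (123 × 48 + 56.8 × 24)/179.8 = 40.4 weeks. Here *r* = 1 − *p*/(−ln(1 − *p*)).

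- *p* = 5%: *r* = 1 − 0.05/0.0513 = 0.0252; printed (6.15 + 1.43)/179.8 = 4.2%.
- *p* = 10%: *r* = 0.0509; printed (12.3 + 2.89)/179.8 = 8.4%.
- *p* = 30%: *r* = 0.1589; printed (36.9 + 9.02)/179.8 = 25.5%.

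**Range for true risks of 5-30%.**

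| Later accrual | *k* | Mean weeks, later children | Share incomplete | Understated, constant hazard | Understated, s = 0.5 to 2 |
|---|---|---|---|---|---|
| Half | 28.4 | 24 | 19% | about 9% | about 6-12% |
| Planned | 56.8 | 24 | 32% | about 15-16% | about 10-21% |
| Double | 57 | 36 | 32% | about 7-8% | about 4-13% |

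At double the rate the 57 children enter within 57/2.37 = 24.1 weeks, so they are further along at the trigger.

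**Effect on the comparison.** With true risks of 10% and 5%, the planned-rate case prints 8.4% and 4.2%. The difference shrinks from 5 to 4.2 points and the ratio stays at 2.0, because randomization within age strata dilutes both arms alike.

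**What the exposure-adjusted rates cover.** SAP 7.6.2 plans them for serious adverse events (all and related), and 7.6.5 for non-serious and all adverse events with incidence of at least 5%. None is planned for discontinuations due to adverse events (7.6.3), Grade 3-4 tables and events under 5% (7.6.5), or laboratory abnormalities and flares (7.6.6.1). If the 5% screen uses the crude percentage, it is diluted too: at the planned rate a true 5.9% prints just under 5%. SAP 8.10 takes exposure as time on study therapy and does not say that it stops at the Week 48 cut. The only Kaplan-Meier analysis is of time on therapy (7.4.1).

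**The case against.** Using every exposed child for safety is a defensible choice, and it is what Protocol section 8.2 requires. SAP section 9 plans a further analysis when all subjects have reached Week 48, with every safety analysis performed, so the problem is confined to one earlier cut. No safety hypothesis test is specified. A reader of the report could see the short follow-up: SAP 7.3.3 counts children continuing treatment, and 7.4.1 tabulates exposure for all treated subjects and for the Primary Cohort. For a rare event the bias is small beside chance: about 0.8 points at a true 5%, against a standard error of √(0.05 × 0.95/120) = 2.0 points on entecavir. For common adverse events, where the absolute bias is larger, exposure-adjusted rates are planned.

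All of this stands. It limits the point and rules out replacing the all-treated tables. It does not make the percentages correct at this cut, or cover the outcomes that have no rate.

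A reader might also infer more than the documents support:

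- That no later child can have reached Week 48. The cohort is at least 123, no data cut-off is stated, and the Week 48 window opens after 42 weeks (SAP 8.4). At the planned rate about 1.18 × 6 = 7 later children could already have a Week 48 value.
- That 31-32% of the denominator is a plan figure. It is an assumed scenario, close to the maximum of 57/180.
- That flare tables run over all treated children. They need at least one laboratory value. With the first scheduled on-treatment sample at Week 4, that removes only about 1.18 × 4 = 5 later children at the planned rate.

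**Conclusion.** The concern holds for crude percentages and absolute differences at the primary analysis only. If accrual after the 123rd child is between half and twice the planned rate, about 19-32% of the denominator has incomplete follow-up. Risks of 5-30% are then understated by about 7-16% in relative terms at constant hazard, and by about 4-21% when events may cluster early or late. The direction is the same in every scenario; the size rests on an accrual rate, a cut-off date and a hazard shape that the plan does not give. A larger Primary Cohort or a later data cut would reduce it.

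It would be wrong to conclude that the treatment comparison is biased in favour of either arm, or that all adverse event results go uncorrected. Ratios are little affected, and serious and common adverse events have exposure-adjusted rates as a partial remedy. The uncorrected outcomes are adverse-event discontinuations, Grade 3-4 tables, less common events, laboratory abnormalities and ALT flares, until all subjects have reached Week 48.

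**What to change.** In SAP section 9, for the primary analysis:

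1. Keep the all-treated safety tables as the main set, in line with Protocol 8.2, and label their through-Week-48 percentages as based on incomplete follow-up.
2. Beside them, add Primary Cohort columns, or Kaplan-Meier Week 48 risks for all treated subjects over blinded time, for adverse events, serious adverse events, adverse-event discontinuations, laboratory abnormalities and ALT flares.
3. State the data cut-off and the number of treated children, by arm, with under 48 weeks of potential follow-up.

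The cost is SAP wording and one extra column set at one analysis; the SAP already plans Primary Cohort baseline and exposure summaries. The added columns rest on about 123 children, so they are less precise: for a 5% risk on entecavir the standard error is √(0.05 × 0.95/82) = 2.4 points rather than about 2.0. The Kaplan-Meier option uses every treated child and avoids that loss.

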## APPENDIX 1 RELEVANT PROTOCOL DEVIATIONS

The relevant protocol deviations that can be programmed from the database are identified below. The list may be updated as appropriate if, in the course of monitoring the study, additional protocol deviations are found and considered relevant. Non-study medications marked below with # are identified by a BMS physician prior to database lock from blinded listings.

### Eligibility Deviations

Eligibility deviations (ie, protocol deviations of entry criteria) are listed below.

- Inclusion 2b: HBeAg negative or missing, or HBeAb positive or missing at screening
- Inclusion 2c: ALT < 1.5 x ULN or  $\geq 10 \times$  ULN or missing at screening
- Inclusion 2d: HBV DNA <  $10^5$  c/mL or missing at screening
- Inclusion 3a: Age < 2 or  $\geq 18$  years
- Exclusion 1d: Women with positive pregnancy test at screening
- Exclusion 2a: Positive test for HIV, HCV or HDV at screening.
  - HCV positive is defined as both HCV antibody positive and detectable HCV RNA.
  - HIV positive is defined as having a positive result for HIV-1 and HIV-2 screen and either HIV-1 confirmation or the HIV-2 confirmation immunoblot.
- Exclusion 4a: Hemoglobin < 10.0 g/dL or missing at screening
- Exclusion 4b: Platelets count <  $70,000/\text{mm}^3$  or missing at screening
- Exclusion 4c: Glomerular filtration rate < 50 mL/min/1.73 m^2 or missing at screening. This is estimated using Schwartz formula.
- Exclusion 4d: Total bilirubin > 2.5 mg/dL (> 42.75  $\mu\text{mol/L}$ ) or missing at screening
- Exclusion 4e: INR > 1.5 or missing at screening
- Exclusion 4f: Albumin < 3 g/dL (< 30 g/L) or missing at screening
- Exclusion 4 g: Alpha fetoprotein  $\geq 50$  ng/mL or missing at screening
- Exclusion 6a: Prior therapy  $\geq 12$  weeks with any anti-HBV nucleoside or nucleotide. This includes, but is not limited to adefovir, tenofovir, famciclovir, clevudine, lamivudine, telbivudine or emtricitabine (#)
- Exclusion 6b: Prior therapy with interferon alpha, thymosin alpha or any anti-HBV nucleos[t]ide antiviral agent within 24 weeks of screening (#)
- Exclusion 6c: Prior ETV

### On-Treatment Protocol Deviations

Protocol deviations during the on-treatment period are as follows:

- Incorrect study therapy received: subjects randomized to active ETV who received PBO or the incorrect active dose; subjects randomized to PBO who received blinded active ETV. Subjects who received the incorrect study therapy during the entire treatment period are further identified.

- Blinded therapy received after not seroconverting at Week 48 (defined as receiving blinded therapy after 54 weeks and not seroconverting at Week 48 based on NC = M)
- Open-label ETV received after seroconverting at Week 48 without seroreversion (defined as receiving open-label ETV after 54 weeks, seroconverting at Week 48 based on NC = M, and seroreverting after Week 48 based on NC = M)
- Average daily dose < 80% of target dose
- Treatment continued after positive pregnancy test (defined as not discontinuing study therapy or discontinuing study therapy > 2 weeks after positive pregnancy test)
- Treatment continued after positive HIV test (defined as not discontinuing study therapy or discontinuing study therapy > 2 weeks after positive HIV test)
- Prohibited concomitant medications (#)

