4.1.1 Subject Management Decisions

Assessment of HBeAg seroconversion will be done, as needed, at Study Weeks:

- 52 (based upon Week 48 result);
- 100 (based upon Week 96 result); and
- 148 (based upon Week 144 result).

The investigators shall conduct the assessment of HBeAg response status at the assessment time points; this will be cross checked centrally by the BMS Medical Monitor/Protocol Manager. Subjects achieving HBeAg seroconversion shall initiate consolidation therapy for an additional 48 weeks as follows:

- At Week 52 (consolidation using blinded therapy to Week 96; 48 weeks counting from Week 48)
- At Week 100 (consolidation using open-label ETV to Week 144; 48 weeks counting from Week 96)
- At Week 148 (consolidation using open-label ETV to Week 192; 48 weeks counting from Week 144)

Subjects who achieve HBeAg seroconversion and revert back to HBeAg-positivity or develop HBeAg-negative CHB shall be managed as follows:

- Any subject who achieves HBeAg seroconversion by the Week 48 assessment and reverts to HBeAg-positive status before reaching Week 96 will be treated with open-label ETV until study Week 144, and then will stop study therapy and proceed to the LTFU phase;
- Any subject who achieves HBeAg seroconversion after the Week 48 assessment, who reverts back to HBeAg-positive status shall stop study treatment, if applicable, and be treated at the discretion of the investigator in consultation with the BMS Medical Monitor.
- Subjects who develop HBeAg-negative CHB (absence of HBeAg, presence of anti-HBe antibodies, active viral replication [HBV DNA by PCR assay $\geq 10,000$ copies/mL] and biochemical or histological evidence of hepatitis) shall be managed at the discretion of the investigator in consultation with the BMS Medical Monitor.

Study treatment (ETV and placebo) shall be provided during the blinded and open-label study treatment phases. Rescue open-label ETV shall be provided to subjects who experience extreme elevations of ALT due to acute exacerbations of CHB upon investigator request and approval by the Central Medical Monitor (see section 4.1.2).

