## 7 STATISTICAL ANALYSES

### 7.1 General Methods

All analyses (efficacy, safety and PK) are presented by treatment regimen, ie, ETV vs PBO, based on the appropriate cohort and dataset defined in the earlier section. For Week 48 analysis, all the endpoints are to be cut off through Week 48, unless specified otherwise.

The PK analyses are described in [Section 7.7](#). The methods described below are used to analyze safety and efficacy data.

Categorical variables are summarized either with counts and percents or with proportions (number with event divided by number evaluable) and percents, depending on the endpoint.

Continuous variables are summarized with univariate statistics (eg, n, mean, median, standard deviation, standard error, quartiles, minimum, and maximum).

Longitudinal analyses of efficacy and safety parameters use pre-defined visit week windows (see [Section 8.4](#)). Windows around planned measurement times are constructed based on the

midpoint between planned measurement visits unless specified otherwise. Data are summarized at each scheduled visit through the analysis week.

Analyses of HBV DNA use values only from the central laboratory from the Roche COBAS® TaqMan HBV Test with limit of quantitation (LOQ) of 29 IU/mL and limit of detection (LLD) of 10 IU/mL.

Analyses of laboratory tests and serology use values from the central or local laboratory. Laboratory parameters are summarized using US standard values and units. Refer to [Section 8.11](#) for conversion of select laboratory test values from the Abbott Architect system to the Roche Diagnostics Hitachi Modular system.

Formats of tables, listings and graphs are described in the Data Presentation Plan (DPP).

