## 7.2 Study Conduct

Relevant protocol deviations are summarized by treatment regimen for treated subjects. Relevant protocol deviations are those that could potentially affect the interpretability of the study results. A list of programmable relevant protocol deviations is provided in [Appendix 1](#), including:

- Eligibility deviations (based on deviations of subject inclusion and exclusion criteria from Protocol Sections 4.2.1 and 4.2.2 which can be programmed from the database) during the pre-treatment period. If multiple measurements are available, a subject is considered to have a deviation only if all measurements fail the inclusion or exclusion criterion, except for pregnancy.
- Deviations during the on-treatment period (eg, incorrect dosing received).
- Deviations related to PK data.

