### **7.3.4 Demographic and Other Baseline Characteristics**

Summaries are presented by as-treated treatment regimen for treated subjects unless specified otherwise. Summaries identify the number and percent of subjects with not reported (i.e., missing) measurements, unless specified otherwise.

If  $\geq 5\%$  of treated subjects have as-randomized regimen different than as-treated regimen, then demographics and baseline disease HBV characteristics are summarized analogously by as-randomized treatment regimen for treated subjects.

Demographic and other baseline characteristics are summarized by treatment regimen and overall for treated subjects:

- Demographics: age (years), age randomization strata ( $\geq 2$  to  $\leq 6$ ,  $> 6$  to  $\leq 12$ ,  $> 12$  to  $< 18$  years), gender, race, ethnicity, geographic region (Asia, Europe, North America, South America), country
- HBV disease characteristics: HBV DNA ( $\log_{10}$  IU/mL), Hepatitis B Surface Antigen (positive, negative, indeterminate), Hepatitis B E Antigen (positive, negative, indeterminate), Hepatitis B E Antibody (positive, negative, indeterminate), HBV genotype (e.g., A, B, C, D, E, indeterminate), INR, albumin (g/dL), ALT (U/L), ALT categories ( $\leq 2 \times$  ULN,  $> 2 \times$  ULN), total bilirubin (mg/dL), creatinine (mg/dL), glomerular filtration rate ( $< 50$ ,  $50 - 75$ ,  $> 75$  mL/min/1.73 m^2) estimated with Schwartz's formula, route of transmission (mother-to-

- child transmission; household/close contact exposure; transfusion; sexual contact; IV drug use; other)
- Physical measurements: height (cm), height for age Z score (HAZ), height for age percentile (HAP), weight (kg), weight for age Z score (WAZ), weight for age percentile (WAP), body mass index (BMI;  $\text{kg}/\text{m}^2$ ), BMI for age Z score (BMIAZ), BMI for age percentile (BMIAP) (see [Section 7.6.7](#))
  - Laboratory tests (see [Section 7.6.6.1](#))
    - Hematology by toxicity grade (ie, normal, Grade 1, 2, 3, 4)
    - Liver function tests by toxicity grade
    - Pancreatic enzymes by toxicity grade
    - Renal function tests by toxicity grade
    - Electrolytes (low and high) by toxicity grade
    - Glucose categories regardless of fasting status
  - Medical history by body system
  - Prior medications, defined as non-study medications taken before the first dose of study therapy.

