#### **7.6.6.1 Laboratory Abnormalities**

For each laboratory test, laboratory abnormalities by toxicity grade (Grade 1 - 4; Grade 3 - 4) on treatment are summarized by treatment regimen and baseline status (all, normal, abnormal, not reported) for the following 3 cohorts:

- Through Week 48 on blinded therapy for treated subjects
- After Week 48 on blinded therapy or on open-label ETV through Week 96 for the Year 2 Safety Cohort
- On ETV treatment for All ETV Safety Cohort

Laboratory tests include:

- Hematology: hemoglobin, platelets, international normalized ratio (INR), white blood cell count (WBC) and neutrophils + bands (absolute)
- Liver function tests: alanine aminotransferase (ALT), aspartate aminotransferase (AST), total bilirubin and albumin
- Pancreatic enzymes: lipase (colorimetric or turbidimetric assay)
- Renal function tests: creatinine and BUN/urea (BUN or urea)
- Electrolytes (low and high): chloride, potassium and sodium.

Toxicity grades are based on DAIDS, unless specified otherwise (see Protocol Appendix 2). BUN/urea and chloride are graded with modified WHO criteria.

Treatment emergent laboratory abnormalities by toxicity grade (increased to Grades 1, 2, 3 and 4) are also summarized analogously by treatment regimen and baseline status for the 3 cohorts. On-treatment emergent abnormalities are those with a higher toxicity grade than the baseline toxicity grade (including not reported baseline).

In addition, the following select laboratory elevations and abnormalities on treatment are summarized by treatment regimen for the 3 cohorts:

- Any Grade 3 - 4 laboratory abnormality (see previous list of tests)
- Liver function elevations  $> 2$  and  $> 3$  x baseline (ALT, AST, total bilirubin)
- Liver function elevations  $> 2$  x baseline and Grade 4 (ALT, AST and total bilirubin; includes ALT flares, defined as ALT  $> 2$  x baseline and  $> 10$  x ULN)
- Simultaneous ALT and total bilirubin elevations (ALT  $> 2$  x baseline, total bilirubin  $> 2$  x baseline and  $> 2$  x ULN; ie, those occurring on the same collection day).

- Albumin < 2.5 g/dL
- Lipase elevations > 3 x baseline
- Confirmed creatinine elevations  $\geq 0.3$  and  $\geq 0.5$  mg/mL from baseline (2 sequential measurement or last measurement meeting the elevation criteria)
- Glucose categories (< 50,  $\geq 200$  mg/dL) regardless of fasting status.

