For PBO-treated subjects who receive open-label ETV, baseline is used during blinded dosing, while ETV baseline is used during open-label ETV dosing.

Laboratory abnormalities by toxicity grade (Grade 1 - 4; Grade 3 - 4) are also summarized by treatment regimen and EOD status (all, normal, abnormal) for the first 2 follow-up cohorts: (1) off-treatment follow-up for off-treatment follow-up subjects in the Post-Year 1 Safety Cohort; (2) long-term follow-up for long-term follow-up subjects in the Post-Year 1 Safety Cohort.

Laboratory abnormalities by toxicity grade (Grade 1 - 4; Grade 3 - 4) are also summarized by treatment regimen during alternative ETV follow-up for alternative ETV follow-up subjects in the Post-Year 1 Safety Cohort.

Emergent laboratory abnormalities by toxicity grade (increased to Grades 1, 2, 3 and 4) are also summarized analogously by treatment regimen and EOD status for the first 2 follow-up cohorts. Emergent abnormalities are those with a higher toxicity grade than the EOD toxicity grade.

Select laboratory elevations and abnormalities are summarized relative to the EOD value for the 3 follow-up cohorts. In addition, elevations of liver function tests (including ALT flares, defined as ALT > 2 x reference and > 10 x ULN) during the follow-up periods are summarized using the reference value (REF) (ie, minimum of the baseline and EOD values) for the 3 follow-up cohorts. Note that for PBO-treated subjects who receive open-label ETV, reference is the minimum of the ETV baseline and EOD values.

ALT multiples of ULN and HBV DNA values are plotted over time for each subject who had an ALT flare on study. The duration of an ALT flare is measured from the first ALT measurement meeting the ALT flare criteria to resolution, defined as (1) the first ALT  $\leq$  baseline or  $\leq 5$  x ULN on treatment, or (2) the first ALT  $\leq$  reference or  $\leq 5$  x ULN during follow-up. If (1) and (2) are not met, an ALT flare is considered unresolved, and the last ALT measurement is used to estimate duration.

The time to and duration of ALT flares (weeks) during off-treatment follow-up are summarized for off-treatment follow-up subjects in the Post-Year 1 Safety Cohort (limited to ETV, PBO OL, and All ETV). Analyses are based on the first ALT flare during off-treatment follow-up.

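### Two SAP programming rules for descriptive tables are wrong as written: one deviation definition contradicts its own name, and the creatinine cut-offs are in mg/mL

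*SAP*

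**What the plan says.** **Deviation rule.** SAP Appendix 1, under On-Treatment Protocol Deviations, names the deviation as "Open-label ETV received after seroconverting at Week 48 without seroreversion". The bracket after the name sets three conditions: open-label ETV after 54 weeks, then "seroconverting at Week 48 based on NC = M, and seroreverting after Week 48 based on NC = M". Protocol 4.1.1 says that a child who seroconverts by the Week 48 assessment and "reverts to HBeAg-positive status before reaching Week 96 will be treated with open-label ETV until study Week 144". Protocol 4.1 otherwise keeps Week 48 seroconverters on blinded therapy through Week 96. SAP 7.2 describes relevant deviations as those that could affect how the results are interpreted, and adds: "Relevant protocol deviations are summarized by treatment regimen for treated subjects".

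**Creatinine rule.** SAP 7.6.6.1 defines confirmed creatinine elevations as rises of at least 0.3 and at least 0.5 "mg/mL from baseline (2 sequential measurement or last measurement meeting the elevation criteria". SAP 7.3.4 lists "creatinine (mg/dL") among the baseline characteristics, and SAP 7.1 states: "Laboratory parameters are summarized using US standard values and units". In the same list in SAP 7.6.6.1, albumin is in g/dL and glucose in mg/dL.

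**The concern.** Appendix 1 presents its list as what can be programmed from the database, so the bracket is the working specification, and here it says the opposite of the name. A program that follows it would report, by treatment regimen, children managed as the protocol directs as deviators. It would omit children who were switched to open-label ETV with no reversion at all.

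The creatinine cut-offs are the SAP's only rule for an absolute rise in creatinine from baseline. The graded creatinine abnormalities use multiples of the upper limit of normal (Protocol Appendix 2). Protocol 5.3.1 notes that ETV is cleared mainly by the kidneys, so a reader will look at these rows. If the printed unit is followed, the rows would be empty in practice and could be taken as reassurance. If a programmer applies 0.3 and 0.5 to a mg/dL variable, the counts come out as intended. The result then depends on a choice that the SAP does not record.

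**Working it through.** The plan derives no figure here; the cut-offs and the deviation rule are simply specified. The check is therefore one of logic and one of units.

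**1. Name against bracket.** Take three yes/no facts: open-label ETV after 54 weeks, seroconversion at Week 48, and later seroreversion. They give 8 combinations. In 6 of them neither the name nor the bracket flags anyone. In the other 2 (open-label ETV yes, Week 48 seroconversion yes) they are opposite:

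- no reversion: the name flags, the bracket does not;
- reversion: the bracket flags, the name does not.

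**2. Adding the order of events.** The bracket sets no order between reversion and the first open-label dose, and it has no Week 96 limit. For Week 48 seroconverters given open-label ETV after 54 weeks, four patterns follow:

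| Pattern | When the child reverted | Status under Protocol 4.1 and 4.1.1 | Bracket as printed | Result |
|---|---|---|---|---|
| A | Before the first open-label dose and before Week 96 | As directed | Flags | Wrong |
| B | Before the first open-label dose, at or after Week 96 | Not settled by the reversion rule | Flags | Undetermined |
| C | Only after the first open-label dose | Deviation | Flags | Right |
| D | Never | Deviation | Does not flag | Wrong |

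The printed rule is right in 1 pattern, wrong in 2 and undetermined in 1. These are patterns, not counts of children.

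**3. Creatinine units.** 1 dL = 100 mL, so:

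- 0.3 mg/mL × 100 = 30 mg/dL;
- 0.5 mg/mL × 100 = 50 mg/dL.

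Each is 100 times the same number in mg/dL.

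**4. Scale, for illustration only.** The Roche column of the creatinine row in SAP 8.11 runs from 46.0 to 128.5 µmol/L. Assume 1 mg/dL of creatinine = 88.4 µmol/L (a unit conversion that the documents do not give):

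- 46.0 / 88.4 = 0.52 mg/dL and 128.5 / 88.4 = 1.45 mg/dL;
- 30 × 88.4 = 2,652 µmol/L, and 2,652 / 128.5 = 20.6;
- 50 × 88.4 = 4,420 µmol/L, and 4,420 / 128.5 = 34.4.

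A rise of the printed size would be about 21 or 34 times the highest value in that comparison.

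**5. Where the cut-offs are used.** They enter the tables for three on-treatment cohorts (SAP 7.6.6.1). They also enter the follow-up tables: "Select laboratory elevations and abnormalities are summarized relative to the EOD value for the 3 follow-up cohorts". SAP 7.6.8 adds breakdowns by four subgroup factors: age stratum, region, HBV genotype and route of transmission.

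**The case against.** The strongest reply is that these are two drafting slips, a lost negation and one wrong unit, with no inferential effect. SAP 6.3 defines no per-protocol set, so a deviation flag excludes nobody. SAP 7.1 and 7.3.4 point a programmer to mg/dL, and the empty rows arise only if those sections are overridden. Graded creatinine and creatinine over time (SAP 7.6.6.2) are unaffected. Few children are likely to be involved, since Protocol 4.1.1 has seroconversion status cross-checked centrally. All of this stands as a limit on the consequences. It does not make either rule correct, and both are instructions for reported tables.

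Three narrower points also deserve weight:

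- The SAP 8.11 range comes from a laboratory method comparison, not from trial children, and is no physiological ceiling. That is correct, so the multiples above show scale only. The 100-fold discrepancy needs neither that range nor the 88.4 factor.
- Pattern B may be a deviation after all: blinded consolidation ends at Week 96, and Protocol 4.1.1 says study drug is not supplied beyond the treatment phase except as rescue. That reading is arguable, which is why B is left undetermined here.
- Inserting a bare negation makes the bracket match the name in all 8 combinations, whereas an ordering condition needs a date rule, because SAP 8.4 and 8.7 select serology by visit window. This is fair as to cost. But the bare negation would leave pattern C, a true deviation, unflagged, so the ordering is worth specifying.

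**Conclusion.** The concern holds on both parts. The deviation bracket contradicts its own name and, taken literally, misclassifies patterns A and D. The creatinine cut-offs are printed 100 times too large if mg/dL was meant. That intention is inferred from SAP 7.1, SAP 7.3.4 and the neighbouring items in SAP 7.6.6.1; the creatinine line itself does not say so.

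The effect is confined to the descriptive deviation summary and the confirmed creatinine elevation rows. Nothing changes for the primary endpoint, its test, the sample size or any analysis population. How many children would be misclassified cannot be worked out from the documents. The corrections should be made before the tables are programmed, but they do not threaten the trial's main conclusion.

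**What to change.** 1. **Deviation bracket (SAP Appendix 1).** Redefine it as: open-label ETV taken after 54 weeks; HBeAg seroconversion observed at Week 48; and no HBeAg seroreversion observed after Week 48 and before the first open-label ETV dose, all on NC = M.
2. **Week 96 limit.** Reconcile the bracket with Protocol 4.1.1 and add one sentence saying how reversion at or after Week 96, followed by open-label ETV, is classified. Without it, the wording in item 1 would leave pattern B unflagged by default.
3. **Date conventions.** State that the order is judged on sample and dose dates. Say how a reversion sample dated the same day as the first open-label dose is treated, and how a child with no serology after Week 48 is classed.
4. **Creatinine (SAP 7.6.6.1).** Change mg/mL to mg/dL.

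The cost is two word-level corrections, one classifying sentence and a short date convention. No new data are needed and no test is affected.
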